9. PROTOCOL REGISTRATION

Patients will be assigned to the protocol by the Clinical Coordinator who will register the patient with the Registration Office, [contact], between 8:30 am and 4:00 pm, Monday through Friday. After hours, the Registration Office can be reached by paging [contact].

10. STUDY AGENTS

10.A. MCPyV-specific CD8 $^{+}$ Cells

10.A.1. Procedure to obtain PBMC for generation of MCPyV-specific CD8 $^{+}$ cells

Patients will have undergone leukapheresis under FHCRC IRB-approved **Protocol 2365** to obtain PBMC for the generation of antigen-specific T cells in the lab. PBMC

may be cryopreserved under therapy conditions and used to generate T cells for this study.

10.A.2. Generation of MCPyV-specific CD8⁺ cells

All T cells administered will be autologous antigen-specific T cells targeting MCPyV TAg and derived from the peripheral blood lymphocytes of a patient with an established diagnosis of MCC. Methods employed to generate and qualify product for infusions are outlined in **IND 14279** (Sponsor [name]). T cells demonstrating antigen specificity are further qualified using mycoplasma, fungal, and bacterial sterility testing.

10.A.3. Handling of T-cell products before infusion

For each infusion, the cell product is formulated at the desired cell dose in a final volume of 500 mL. The final product will be prepared and labeled according to standard of operation procedure in the Cellular Processing Facility. The cell product will be transported to the infusion facility by a protocol delegated staff member. During the time of transportation the cell product will be kept in a cooler with a cool pack. A nurse will then administer the cells to the patient over one to two hours (as described in **Section 11.4**).

10.B. Anti PD-L1 Antibody Avelumab

10.B.1. Packaging and labeling

Avelumab is a sterile, clear, and colorless solution intended for IV administration supplied by the Sponsor in single-use glass vials at a concentration of 20 mg/mL closed with a rubber stopper and sealed with an aluminum yellow polypropylene flip off seal. Packaging and labeling will be in accordance with applicable local regulatory requirements and applicable Good Manufacturing Practice (GMP) guidelines. Avelumab will be packed in boxes containing a suitable number of vials. The information on the IMP will be in accordance with approved submission documents. Avelumab will be shipped in transport cool containers (2°C to 8°C) that are monitored with temperature control devices.

10.B.2. Storage, handling, and preparation

The contents of the Avelumab vials are sterile and nonpyrogenic, and do not contain bacteriostatic preservatives. Any spills that occur should be cleaned up using the facility's standard cleanup procedures for biologic products.

Avelumab drug product must be stored at 2°C to 8°C until use, with a temperature log maintained daily. All medication boxes supplied to each trial site must be stored carefully, safely, and separately from other drugs.

Avelumab drug product stored at room temperature (23°C to 27°C) or at elevated temperatures (38°C to 42°C) for extended periods is subject to degradation.

Avelumab must not be frozen. Rough shaking of Avelumab must be avoided. For application in this trial, Avelumab drug product must be diluted with 0.9% saline solution (sodium chloride injection) supplied in an infusion bag. Detailed information on infusion bags and medical devices to be used for the preparation of the dilutions and subsequent administration will be provided in the MOP.

Avelumab must not be used for any purpose other than the trial. The administration of IMPs to subjects who have not been enrolled into the trial is not covered by the trial insurance.

Any unused portion of the solution should be discarded in biohazard waste disposal with final disposal by accepted local and national standards of incineration.

10.B.3. Avelumab product accountability

The Investigator is responsible for ensuring accountability for IMP, including reconciliation of drugs and maintenance of drug records.

- Upon receipt of IMP, the Investigator (or designee) will check for accurate delivery and acknowledge receipt by signing (or initialing) and dating the documentation provided by the Sponsor and returning it to the Sponsor. A copy will be retained for the Investigator File.
- The dispensing of the IMP will be carefully recorded on the appropriate drug accountability forms provided by the Sponsor and an accurate accounting will be available for verification by the Sponsor's Monitor at each monitoring visit.
- IMP accountability records will include:
 - confirmation of IMP delivery to the trial site;
 - the inventory at the site of IMP provided by the Sponsor and prepared at the site;
 - the use of each dose by each subject;
 - the return to the Sponsor or alternative disposition of unused IMP; and
 - dates, quantities, batch numbers, expiry dates and (for IMP prepared at the site) formulation, as well as the subjects' trial numbers.
- The Investigator should maintain records that adequately document
 - that the subjects were provided the doses specified by the clinical trial protocol/amendment(s); and
 - That all IMP provided by the Sponsor was fully reconciled.

Unused IMP must not be discarded or used for any purpose other than the present trial. Any IMP that has been dispensed to a subject must not be redispensed to a different subject.

The Sponsor's Monitor will periodically collect the IMP accountability forms and will check all returns (both unused and used containers) before arranging for their return to the Sponsor or authorizing their destruction by the trial site.

At the conclusion or termination of this trial, trial site personnel and the Clinical Trial Monitor (CTM) will conduct a final product supply inventory on the Investigational Drug Accountability Forms and all unused containers will be destroyed. Instructions for destruction of product will be provided to the site. The CTM will be supplied with a copy for filing of the Investigational Drug Accountability Forms. This documentation must contain a record of clinical supplies used, unused, and destroyed and shall include information on

- all administered units,
- all unused units,
- all destroyed units (during the trial),
- all destroyed units at the end of the trial,
- date of destruction(s),
- name and signature of the Investigator/pharmacist.

It must be ensured at each trial site that the IMP is not used

- after the expiry date, and
- after the retest date unless the IMP is reanalyzed and its retest date extended.

This is to be closely monitored by the trial monitor.

10.C. Radiation therapy

The goal of the radiation is not to kill tumor cells, although some lesional stabilization/shrinkage is expected in many cases, but to induce the tumor cells to up-regulate previously down-regulated MHC Class I to prime a systemic immune response mediated by the transferred CTL. A suggested regimen based on a large case series as well as preclinical data supporting MHC upregulation effect is 8 Gy dose given in single fraction,⁵³ however we recognize that there are clinical scenarios in which alternate dosages and/or fractionated regimens may be more appropriate, and in this scenario the treating radiation oncologist may select an alternate regimen for the patient if felt that it is in the best interest of patient safety. Given that radiation is being given for MHC Class I upregulation/antigen presentation, the GCT (gross tumor volume) and the CTV (clinical tumor volume) are the same. For the planning tumor volume (PTV) which accounts for

day-to-day set-up variations, it is recommended a 5-10mm margin be added to the GTV (subject to individualization by the treating Radiation Oncologist). CT-based 3D-conformal planning (e.g. Intensity Modulated Radiation Therapy [IMRT]) will be utilized to minimize dose to the surrounding critical structures. Image Guided Radiotherapy (IGRT) will be utilized to verify the target location at treatment with the planning CT scan. Choice of radiation modality will be at discretion of radiation oncologist. It is recommended that the field size be kept under 10 x 10 x 10 cm. Re-irradiation is allowed although it is recommended to limit re-irradiation to the spinal cord, neural structures and small bowel to no more than 2x single fraction 8Gy radiation unless no appropriate alternatives. Radiation will be completed within 2 to 5 days prior to a T-cell infusion and 7 to 4 days prior to the infusion of the next anti-PD-L1 infusion.

If MHC class I up-regulation is not clinically indicated, (for example tumor site reduction without clearance and/or no discrete tumor metastasis that can be irradiated or infiltrated with intralesional IFN β -1B) the second set of T cell infusions can proceed without MHC class I up-regulation.

10.D. Intralesional IFN β -1B Injection

[figure not shown]
IFN β -1B (Betaseron, Bayer, Montville NJ; or Extavia, Novartis, East Hanover, NJ) will be used. One vial contains 0.3 mg or approximately 10×10^6 IU. The lyophilized contents will be suspended in the provided 1.2 ml sodium chloride 0.54%. 1/3 of the vial (0.1mg or approximately 3.3×10^6 UI or 0.1mg) is administered intralesional into an identified lesion after US-guided tumor core biopsy. IFN β -1B administration will be completed 2 to 5 days prior to a T-cell infusion and 7 to 4 days prior to the infusion of the next anti-PD-L1 infusion.

10.E. Guidelines for selecting radiation therapy or intralesional IFN β -1B Injections

The decision to proceed to radiation of the lesions or administer intralesional IFN β -1B will be based on clinical judgment with the following guidelines: 1. If more than one tumor lesions are present at different locations and no critical organ is involved, if feasible, approximately 50% of the lesions should receive radiation or intralesional IFN β -1B initially; 2. At a given time, one patient should receive either radiation or intralesional IFN β -1B but not both modalities; 3. Intralesional IFN β -1B is the preferred modality for patients who have easily palpable superficial lesions (cutaneous, subcutaneous, or lymph nodal metastasis) that can be accurately localized, stabilized by palpation, and are superficial enough to enable intratumoral injections, or patients who have lesions that are attainable through endoscopy; 4. Radiation to a specific lesion or to multiple lesions within a specific field will be administered in the case that multiple radiographically detectable lesions are identified on the pre-treatment scans, lesions are inaccessible by interventional radiology, or the patient refuses intralesional injections. 5. If multiple lesions are present within a tight field, it is recommended not to irradiate some and not others, but rather deliver radiation to the whole field.

11. PLAN OF TREATMENT

Group 1

Group 2

[figure not shown]

Figure 14. Treatment schema

1. Initial Evaluation/Consent (all Groups)

Patients will be screened for their eligibility on the study and consented during this visit. Baseline anthropometry will be obtained.

2. Administration of Avelumab (Groups 1 and 2)

Subjects will receive an IV infusion of Avelumab within 4 weeks of the baseline staging scans at a dose of 10 mg/kg over the duration of 1 hour (-10/+20 minutes) following pretreatment with H1 blockers (diphenhydramine 12.5mg to 50 mg PO or IV, or equivalent), and acetaminophen po 500 to 650 mg, once every 2 weeks (See **Appendix B**). The dose of Avelumab will be calculated based on the weight of the subject determined at trial entry. Following Avelumab infusions, subjects will be observed for 1 hour post infusion for potential infusion-related reactions. Subjects will receive Avelumab once every 2 weeks for 12 months or until the criteria in **Section 13.G.** (Off Study Criteria) are met. Modifications of the infusion rate due to infusion-related reactions are described in **Section 13.C.**

In this trial, subjects will receive Avelumab IV infusions at the SCCA. Well trained medical staff will monitor and perform the trial drug administration.

3. MHC class I up-regulation: Radiation or intralesional IFN β -IB injection

Radiation therapy or intralesional IFN β -1B injection will be scheduled as an outpatient treatment at the SCCA or the University of Washington Medical Center (UWMC) between 7 and 10 days after the preceding dose of Avelumab (for Groups 1 and 2) and within 2 to 5 days prior to a subsequent T-cell infusion (Group 2).

4. T-Cell Infusions

T-cell infusions will be given at the Seattle Cancer Care Alliance at least 48 hours after MHC class I upregulation and preferably at least 48 hours before the next dose of Avelumab. All patients will be observed for 2 hours post infusion and will be released if no AE requiring prolonged hospitalization have occurred (see **Section 13**).

T cells will be infused intravenously at a rate of not more than 500 cc/hour through an 18- or 20-gauge catheter inserted into a peripheral vein or through a central catheter. The infusion bag will be gently mixed periodically during the infusion. Subjects will have vital signs per **Section 12.B**.

12. EVALUATION

See **Protocol Appendix B** for a summary of patient evaluation for Groups 1 and 2. The dates listed on the study calendar are approximate as many patients reside out of the area and may not always follow the time points as dictated by the protocol. Results of tests and, or procedures conducted as standard of care may be used for research purposes. Potential patients will initially be identified and recruited through the SCCA MCC clinic. The informed consent form will be discussed and signed in the presence of a GCP-trained investigator. Patients who are found eligible to participate in this protocol will be followed closely by a multidisciplinary oncology team that includes medical oncologists, dermatologists and radiation oncologists (as appropriate).

12.A. Patient Evaluation at Each Planned Visit

Patients will have a history taken, ECOG performance status (Appendix A), a physical exam with vital signs prior to the T-cell infusion and 1, 14, and 28 days after each infusion. Thyroxine 3 (T3), free thyroxine 4 (FT4) and thyroid stimulating hormone (TSH) at baseline, at cycle 6 and then every 6 cycles. Merkel virus oncoprotein serology at baseline and at time of radiographic evaluation. A comprehensive chemistry panel, and a complete blood count at each planned visit including the pre-treatment visit, prior to Avelumab infusion, prior to IFN β -IB injections or radiation, prior to tissue biopsy or aspiration, prior to the T-cell infusion and 1, 3, 7, 14, and 28 days after each T cell infusion (Appendix B). It is anticipated that some patients reside outside of the area and

may have their +7, +14 and +28 day clinical evaluations completed locally (visits can occur +/- 1 day, weekly visits can occur +/- 3 days before or after the planned date).

12.B. Patient Evaluation During T-Cell Infusions

Blood pressure, heart rate, temperature, respiratory rate, and O₂ saturation (by pulse oximetry) will be recorded at time 0, every 15 minutes during the 1 to 2 hour T-cell infusion, end of infusion, hourly for 2 hours following the T-cell infusion. Adverse events will be managed by standard medical practice (see also **Section 13**).

12.C. Clinical and Laboratory Evaluation for Toxicity (General Toxicity Assessment)

The period of monitoring for treatment-related toxicity will start with the first Avelumab infusion. All grade ≥ 3 CTCAE v.4.03 AEs will be recorded up to the last T cell or avelumab infusion. Beginning 4 weeks after the last study infusion, only study related toxicities will be collected per section 15. To evaluate for potential toxicities, patients will undergo a history and physical and, or laboratory evaluations (comprehensive chemistry panel and complete blood count) immediately prior to Avelumab infusion, prior to radiation therapy or intralesional IFN β -1B injection, immediately prior to infusions, days +1, +3, +7, +14, and +28 after each T cell infusion, and then as clinically indicated after the last infusion (for example, every 3 months for the first year, every 6 months for a year and then yearly see **Appendix B**). Clinical assessments at days +7, +14 and +28 after T-cell infusions may be performed by the patient's local provider and records assessed by the investigator within 14 days for any toxicities not previously assessed.

12.D. Efficacy Assessment

12.D.1. Clinical response by 'median time to new metastasis' (primary endpoint)

All patients treated on this protocol will have developed metastatic disease. It is plausible that up-regulation of MHC class I with either radiation therapy or intralesional IFN β -1B injection may have an independent effect on the targeted metastasis (as assessed by RECIST criteria). It is unlikely however, that localized radiation or intralesional interferon will have a significant effect on the risk of distant disease development. In contrast, T-cell infusions and/or anti-PD-L1 have the potential to generate a broader systemic effect by preventing the occurrence of new distant metastasis. To assess the potential systemic effects of adoptively transferred T cells, the time for a new metastasis to develop after treatment will be assessed, and this parameter will be compared to historical matched controls undergoing standard therapy. A preliminary assessment was carried out on 49 of the MCC patients in our cohort who originally presented with local or regional disease and later developed metastatic disease, at which time they underwent standard therapy (radiation or chemotherapy). Patients with systemic immune suppression were eliminated from the analysis as they would not be candidates for the combined MHC and T-cell therapy trial. Among these patients, the median time to developing a new metastasis was 200 days (see **Section**

18 for further statistical details). Patients will be followed and restaged at least once every 3 months and as clinically indicated after 12 months since the last infusion has elapsed until new metastasis occur (see **Appendix B**).

12.D.2 Clinical response by RECIST criteria (secondary endpoint)

Tumor lesions and tumor responses will be assessed according to the **Response Evaluation Criteria in Solid Tumors (RECIST) v 1.1**. Radiographic imaging and clinical assessment of residual disease will be compared with pre-infusion assessment.

Responses will be reported separately for lesions which did or did not receive MHC Class I upregulation interventions, if the latter are present. Overall responses will be reported as well.

Clinical response assessment of each individual lesions: Response assessment will be done through clinical (for example bi-directional measurements of palpable lesions) or radiographic (for example CT, PET, or MRI) measurement of each lesion at 8 weeks after the first intervention to induce MHC class I upregulation, 8 weeks after the second MHC class I upregulation, if the patient undergoes a second set of T cell infusions, and then at least once every 3 months (12 weeks) or as clinically indicated. Consistency of imaging modality over time is recommended for a given patient. Objective responses in lesions which received MHC Class I upregulation and lesions which did not receive MHC Class I upregulation, will be reported separately. For each individual lesion or group of lesions, a complete response (CR) will be defined as total regression of the lesions, a PR as 30% or greater decrease in the sum of the longest diameter of the lesions compared to baseline and PD as 20% increase in the sum of the longest diameter of the lesions compared to the smallest prior diameter (RECIST v1.1 criteria).

Overall Response Assessment:

A complete response (CR) will be defined as total regression of all tumors, a PR as 30% or greater decrease in the sum of the longest diameter of target lesions compared to baseline and PD as 20% increase in the sum of the longest diameter of target lesions compared to the smallest prior diameter (RECIST v1.1 criteria). This assessment will be performed 8 weeks after the first MHC class I upregulation, 8 weeks after the second MHC class I upregulation, if the patient undergoes a second set of T cell infusions, and then at least once every 3 months (12 weeks) or as clinically indicated.

12.E. Evaluation of Persistence and Function of Adoptively Transferred T Cells

12.E.1. Blood samples

Patients will have 50-60 ml of heparinized blood (green top) and 6 ml of serum (red top) tube drawn during the pre-treatment visit, prior to Avelumab infusion, prior to receiving radiation or intralesional IFN β -1B injections (pre-treatment baseline), prior to tissue biopsy or aspiration, prior to infusion, and at selected time points following infusion (**Appendix B**, research labs). Samples will be used to evaluate the duration of *in vivo* persistence and function of infused T cells, as well as evaluation of MCPyV TAg titers.

All blood samples will be kept at room temperature and sent to room E1-305, FHCRC Research Cell Bank.

12.E.2. Tumor samples

Only patients with histologically confirmed MCC will be enrolled on the study. It is anticipated that most patients will undergo a confirmatory biopsy of metastatic lesions; although this may not be possible for patients with a high clinical likelihood of metastatic Merkel carcinoma and lesion(s) that are difficult to access. Patients undergoing intralesional IFN β -1B injections will have an aspirate or biopsy prior to the injections. When obtained, the aspirates or biopsies will serve as a pre-treatment baseline for the presence of MCPyV TAg-specific cells. Localization of transferred MCPyV TAg-specific CTL to tumor sites after treatment will be evaluated in selected patients with surgically accessible disease (disease that is accessible by needle or core biopsy, or that can be excised from skin or superficial lymph node).

Post study treatment biopsy will be done at approximately 4 weeks after the first Avelumab infusion (group 1) and two weeks after the first T cell infusion (group 2). If accessible a 2nd post treatment biopsy may be performed if patients undergo another cycle of MHC class I up-regulation and CTL infusions. If enough material is obtained, single cell suspensions will be prepared and stained to identify antigen-specific CTL by tetramer analysis. Alternatively, if limited material is obtained, DNA will be isolated from samples and used for high throughput TCR analysis. All results will be compared to pre-treatment peripheral blood and, where possible, to pre-infusion tumor samples.

12.E.3. Assessment of the Functional Capacity of Transferred Cells

To evaluate the direct *ex vivo* function of the transferred cells, where possible, tetramer⁺ cells within collected PBMC will be evaluated for production of intracellular cytokines including IFN β , TNF α and IL-2 in response to cognate antigen using an intracellular cytokine assay (ICS).

Intranuclear Ki-67 expression will be assessed on infused tetramer⁺ T cells to evaluate the *in vivo* proliferation of the transferred cells. To evaluate the *ex vivo* proliferative capacity of infused cells compared to the infusion product, carboxyfluorescein succinimidyl ester (CFSE) dye dilution in response to peptide stimulation will be used.

The phenotype of tetramer⁺ antigen-specific cells in the peripheral blood will also be assessed using established immunophenotyping panels including assessment of CD45RO (memory T cells), CD28, CD27, CD127, CD62L and CCR7 (central memory T cells), CTLA-4 (CD152), PD-1, Tim-3, and CD57 (evidence of negative regulation or senescence).

The persistence, function, proliferative capacity and phenotype of infused T cells will be correlated to clinical responses.

12.F. Assessment of Epitope Spreading

Quantification of the overall recognition of the MCPyV T-antigen for each patient will likely be performed by testing the reactivity of whole PBMC before and at indicated timepoints after treatment to peptides 15 amino acids (aa) in length offset by 5 aa bases spanning the whole T-antigen protein to include both CD8 and CD4 responses regardless of the HLA type of the patient. The reactivity will be detected using IFN γ secretion in a human IFN γ ELISpot assay.⁷⁶ Results will be presented as the number of spot forming cells/10⁵ PBMCs.

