- there was no difference in terms of safety for any of the 3 doses, which was consistent with the findings reported for another anti-PD-L1 monoclonal antibody (0.3 to 10 mg/kg), in which the spectrum, frequency, and severity of treatment-related TEAEs were similar among the dose levels, with the exception of infusion reactions (29);
- the finding that the $t_{1/2}$ for the 3 and 10 mg/kg doses were nearly identical is consistent with the view that the target-mediated clearance was saturated and that higher doses were not expected to result in a higher percentage of TO.

3.J. Rationale for Assessing T-Cell Effectiveness by ‘Time to New Metastasis’

It cannot be excluded that up-regulation of MHC class I with either radiation therapy or intralesional IFN β -1B injections may have an independent effect on the targeted metastasis, which could then be measurable by Response Evaluation Criteria In Solid Tumors (RECIST) criteria. Furthermore, as transferred T cells circulate systemically, their effect may be better assessed by the prevention of the establishment of micrometastasis and the occurrence of new detectable metastatic lesions. To capture the systemic effects of adoptively transferred T cells, the time for new metastasis to develop after treatment will be assessed, and this parameter will be compared to historical matched controls undergoing standard therapy by radiation or chemotherapy.

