18. STATISTICAL CONSIDERATIONS

The **primary objective** of this trial is to assess and compare the safety and potential efficacy associated with treating patients who developed metastatic MCC by combined MHC up-regulation and anti-PD-L1 antibody treatment (Group 1); and combined MHC up-regulation, anti-PD-L1 antibody treatment, and adoptive transfer of MCPyV TAg-specific polyclonal autologous CD8⁺ T cells (Group 2). The treatment for each group will be considered to have an acceptable safety profile, if the observed toxicity rate is consistent with a true rate that does not exceed 30%, whereas toxicity is defined in **Section 13**. The potential efficacy of treatment within each group will be assessed primarily by examining the time from first to second metastasis. Among 49 patients who would be considered eligible for this trial and who received standard treatment (localized radiation or chemotherapy) at UW, the median time to second metastasis was an estimated 200 days (**Figure 146**). This is the benchmark that we shall use in the current trial for assessment of potential efficacy.

[figure not shown]

Figure 146. Observed and predicted times to second metastasis

A total of 20 patients will be treated in the trial, including 10 in each of Groups 1 and 2 as long as the level of safety is deemed to be acceptable. This number was not derived based on any formal statistical considerations; rather, it is a number that is a compromise between the number of patients that can be enrolled in a reasonable time frame and the number of patients whose treatment will provide enough information to gain a preliminary assessment of efficacy. From our database of over 850 patients, we are in active contact with ~300 living MCC patients. Approximately 120 new patients are recruited each year to our cohort. One-third of MCC patients will have a first metastasis within 3 years of diagnosis. Each year, approximately 40 patients in our cohort experience a first metastasis. Because we now have tetramers that cover >80% of MCC patients based on their HLA alleles, we anticipate that generation of functional tetramer-positive MCPyV-specific T cells from the peripheral blood will be feasible on a sufficient number of cases so that we can readily meet targeted enrollment of four cases per year.

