The observed time to second metastasis for the 49 patients is summarized in **Figure 146**. Based on these data, and in collaboration with our study biostatistician ([name]), we fit a piecewise exponential model wherein we assumed a constant hazard of metastasis in each of nine different time windows as a means of specifying an assumed-true distribution for time to metastasis. At the end of each window, the assumed-true probability of metastasis is required to equal the observed value at this time. From this assumed-true distribution, the assumed-true distribution for the current

therapy was generated by assuming a hazard of failure that is proportional to that from the assumed-true distribution from the historical data. From this distribution, 5,000 simulated trials were randomly generated, and the lower limit of a point-wise confidence interval was estimated for each simulated trial. The proportion of trials where this confidence limit exceeded 200 days was taken as the estimated power to observe a statistically significantly improved median time to metastasis compared to the fixed time of 200 days. **Table 8** below summarizes the power estimated in this manner for a variety of assumed-true distributions and one-sided significance (α) levels with 10 patients.

Therefore, with 10 patients treated, we'll have sufficient power to observe a statistically significant improvement in median time to metastasis relative to the fixed historical time of 200 days for scenarios with assumed-true parameters as summarized above. For the analysis, we will use 'Time 0' as the first day of treatment as opposed to the time of 1st metastasis. Potential efficacy of Groups 1 and 2 will be assessed in this manner. If each group is deemed to be potentially efficacious, then we will use a "play-the-winner" approach to choose the treatment that will move forward to our next trial, wherein the group with the longest median time to metastasis will be declared the winner. If only one group is deemed to be potentially efficacious as described above, then this is the treatment that will be taken forward. If neither treatment is considered to be potentially efficacious, then neither treatment will be taken forward.

Table 8. Power estimates

Assumed-true Median	Assumed-true Hazard Ratio	Significance level of 0.10	Significance level of 0.15
352 days	3	70%	88%
411 days	4	85%	92%

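### Comparing time to new metastasis with 200 days can assess only each complete regimen; Sections 3.J and 12.D.1 credit it to the T cells, and Section 18 plans no Group 2 to Group 1 estimate

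*Combined protocol and SAP*

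**What the plan says.** Section 3.J, whose heading presents it as the rationale for judging T-cell effectiveness, says of time to new metastasis that "this parameter will be compared to historical matched controls undergoing standard therapy by radiation or chemotherapy". Section 12.D.1, which defines the primary efficacy endpoint, repeats this: "To assess the potential systemic effects of adoptively transferred T cells, the time for a new metastasis to develop after treatment will be assessed". Just before that sentence, 12.D.1 states that "T-cell infusions and/or anti-PD-L1 have the potential to generate a broader systemic effect by preventing the occurrence of new distant metastasis".

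Section 11 gives avelumab to Groups 1 and 2 alike. Section 6 gives both groups MHC class I up-regulation and reserves the T cells for Group 2. Assignment is by HLA type and by whether a T-cell product can be made.

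Section 18 assesses the treatment within each group. Its benchmark comes from 49 patients "who received standard treatment (localized radiation or chemotherapy) at UW", among whom "the median time to second metastasis was an estimated 200 days". Each group is tested separately against that fixed value. If both pass, the group with the longer median is chosen. Otherwise: "If only one group is deemed to be potentially efficacious as described above, then this is the treatment that will be taken forward". Section 4.A makes it a primary objective to assess and compare antitumor efficacy between the groups.

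**The concern.** The comparison described in 3.J and 12.D.1 differs from its controls in more than the T cells. The trial regimen adds avelumab as well, and 12.D.1 names anti-PD-L1 as a possible cause of the outcome being measured. The protocol considers whether radiation or interferon could confound the reading, and chooses this endpoint over RECIST for that reason. It does not apply the same caution to avelumab. Section 3.I.1 reports objective response rates of 7% to 38% for PD-1/PD-L1 blockade in solid tumors, so an avelumab contribution is plausible on the protocol's own account, although a response rate is not an effect on time to new metastasis.

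At stake is what a Group 2 result above 200 days means. Under the wording of 3.J and 12.D.1 it would bear on the T cells. Under the comparison actually made it bears on avelumab, MHC up-regulation and T cells together. The only contrast in the trial that isolates the T cells even roughly is Group 2 against Group 1, and Section 18 plans no estimate of it. Two separate tests against 200 days do not supply one, because one group passing while the other fails is not evidence that they differ.

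**Working it through.** **Inputs from Section 18.** "A total of 20 patients will be treated in the trial, including 10 in each of Groups 1 and 2"; a fixed benchmark of 200 days; a group passes if the lower confidence limit of its median exceeds 200 days; one-sided levels 0.10 and 0.15; treatment hazard proportional to the historical hazard.

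**Assumptions.** Complete follow-up to day 200, and historical S(200) = 0.5. The interval method is not stated, so the pass rule is reconstructed as at most 2 of 10 events by day 200 (0.10 level) or at most 3 of 10 (0.15 level). Log-log, logit and null-variance intervals give these thresholds. Plain, log and arcsine intervals give 3 of 10 at both levels; an exact sign test gives 2 of 10 at both.

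**Formula.** For an h-fold hazard reduction, the event probability by day 200 is q = 1 − 0.5^(1/h), and P(pass) = P(X ≤ k), X ~ Binomial(10, q), with k = 2 or 3.

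**Table 8 first.** At h = 3, q = 1 − 0.7937 = 0.2063. The terms for 0, 1, 2 and 3 events are 0.099, 0.258, 0.302 and 0.209, giving 65.9% for k = 2 and 86.8% for k = 3; Table 8 has 70% and 88%. At h = 4 the results are 79.6% and 94.0%; Table 8 has 85% and 92%. The 0.15 column agrees within 2 points. The 0.10 column is 4 to 5 points lower, more than the error of 5,000 simulations (about 0.6 points). The interval method, the cut-points of the nine windows and any censoring are not in the text, so Table 8 is not called wrong.

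**Illustration: all benefit from avelumab, T cells adding nothing.** Both groups then have the same hazard.

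| Assumed avelumab hazard reduction | P(Group 2 passes), k = 2 | k = 3 |
|---|---|---|
| none | 5.5% | 17.2% |
| 1.5-fold | 22% | 46% |
| 2-fold | 40% | 67% |
| 3-fold | 66% | 87% |
| 4-fold | 80% | 94% |

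**Full Section 18 rule at 3-fold, groups identical.** With p = 0.659 or 0.868:

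- Exactly one group passes: 2p(1 − p) = 45% or 23%.
- Group 2 goes forward: p(1 − p) + p²/2 = 44% or 49%, taking either median as equally likely to be the longer.

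**Precision of Group 2 against Group 1.** If all 20 patients have an event, SE(log HR) ≈ √(4/20) = 0.447. A 90% interval around a hazard ratio of 1 is exp(±1.645 × 0.447) = 0.48 to 2.09.

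**The case against.** The strongest reply is that Section 18 governs the analysis and never calls the Group 2 comparison a test of T cells. It defines each group by its full regimen, tests that regimen against standard therapy, and chooses a regimen for the next trial. The sentences in 3.J and 12.D.1 mainly explain why new metastases are preferred to RECIST when some lesions are irradiated or injected, and 12.D.1 openly names anti-PD-L1 beside the T cells. The design also contains Group 1, a concurrent group with avelumab and no T cells. All of this stands, and it confines the fault to the attribution in 3.J and 12.D.1 and to the missing contrast in Section 18.

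A reader might infer from the table that the plan has a T-cell test with a false-positive rate of 66% to 87%. The documents do not support that. The 3-fold reduction is a Table 8 alternative for the whole regimen, not a documented avelumab effect. If avelumab did work that well, passing would be the correct answer to the question Section 18 asks, so these figures are power. Nor does Section 18 say that a Group 2 pass will be reported as T-cell effectiveness. Likewise, 44% to 49% for Group 2 going forward is simply what a pick-the-winner rule gives when two equal groups usually pass.

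It is also fair to say that the added contrast is weak: not randomised, 10 against 10, and with Group 1 patients able to resume on Group 2 after progression (Section 6). That argues for an exploratory label and a rule for those who switch, not for leaving the contrast out.

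**Conclusion.** The concern holds as a mismatch between stated purpose and comparison. Read as 3.J and 12.D.1 direct, a Group 2 result above 200 days would be credited to the T cells although avelumab alone could produce it. Section 18 tests the right thing for a regimen, but leaves the between-group part of primary objective 2 without an estimate or interval.

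The size depends on an avelumab effect that the documents do not give. Over assumed reductions of 1.5-fold to 4-fold, the chance that Group 2 passes with inert T cells runs from 22% to 80% at the 0.10 level and from 46% to 94% at the 0.15 level. At 3-fold, identical groups would split, one passing and one failing, in about 45% or 23% of trials. These figures rest on 10 patients per group, complete follow-up and the reconstructed pass rule. Table 8's own power at 3-fold (70%/88%) supports the same conclusion without that reconstruction. The attribution problem itself needs no arithmetic.

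**What to change.** - **Sections 3.J and 12.D.1:** say that the comparison with 200 days assesses each complete regimen (avelumab plus MHC up-regulation, with or without T cells) against standard therapy. Remove the statement that it assesses the T cells, and adjust the 3.J heading to match.
- **Section 18, estimate:** add the Group 2 to Group 1 hazard ratio for time to new metastasis with an 80% or 90% confidence interval, labelled exploratory because assignment is by HLA type and product availability.
- **Section 18, switching:** analyse patients by the group in which treatment started. Keep Group 1 patients who resume on Group 2 in Group 1, and add a sensitivity analysis censoring them at the switch. Because Section 6 ties the switch to progression, that censoring may be informative, so it should not be the main analysis.
- **Section 18, interpretation:** state that passing 200 days in Group 2, or in Group 2 alone, is not by itself evidence of a T-cell effect.

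The forward rule may stay as a choice of regimen. The cost is wording in three sections and one model on data already collected. The downside is a weaker T-cell statement, since the interval will be wide even with events in all 20 patients.
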